5.2. Exclusion Criteria

Prospective participants are excluded from the study if **any** of the following criteria apply:

Medical Conditions

1. Has symptomatic visceral disease or any disease burden that makes the participant ineligible for endocrine therapy, per the Investigator's best judgment.
2. Has peritoneal carcinomatosis.
3. Has inflammatory breast cancer at Screening.
4. Has CNS involvement, **unless** participant is at least 4 weeks from prior therapy completion to starting study treatment, has stable CNS tumor at the time of Screening, and is not receiving steroids and/or enzyme-inducing anti-epileptic medications for brain metastases.
5. Has any clinically significant, uncontrolled heart disease and/or cardiac repolarization abnormality.
6. Has a history of prolonged QT syndrome or Torsades de Pointes.

Prior/Concomitant Therapy

7. Has received prior treatment with chemotherapy (**except** neoadjuvant/adjuvant chemotherapy), or with any CDK4/6 inhibitor.
8. Has received prior treatment with fulvestrant.
9. Use of systemic estrogens (eg, hormonal contraception, HRT).
10. Is currently receiving any of the following substances and cannot be discontinued 14 days prior to starting lerociclib:
 - Known strong or moderate CYP3A inducers or strong inhibitors of CYP3A

- Substances that have a narrow therapeutic window and are predominantly metabolized through CYP3A4/5
11. Has evidence of active bacterial infection, fungal infection, or viral infection (including SARS-CoV-2 or uncontrolled HIV, as noted below) which would preclude safe enrollment in the judgment of the Investigator.
- **Notes:**
 - The study SARS-CoV-2 requirements are determined by institutional standards (and local/country regulations, as applicable).
 - At Investigator discretion, any participant who tests positive and/or is symptomatic for SARS-CoV-2 during Screening may either be excluded from the study or delay enrollment until active infection has been excluded per institutional standards.
 - During the study, any SARS-CoV-2 testing is to be performed as clinically indicated for the individual participant. The Investigator must document the results of all tests performed. Any confirmed infection is to be recorded as an AE or, in the event that clinical manifestation warrants such, recorded and handled as an SAE as detailed in [Appendix 3](#).

Diagnostic Assessments

12. Ejection fraction of $\leq 45\%$ on echocardiogram performed within the past 12 months, or documented history of congestive heart failure with reduced ejection fraction.
13. Oral temperature of $> 38^{\circ}\text{C}$ at Screening, or any evidence of SARS-CoV-2 infection.
14. Interstitial pneumonia or severe impairment of lung function, with the latter defined as having vital capacity AND DLCO that are $\leq 50\%$ of the normal predicted values OR having an O_2 saturation at rest in ambient environment of $\leq 88\%$.

5.3. Lifestyle Considerations

No restrictions are specified.

Based on current available data, lerociclib may be administered without regard to food; however, dosing under fed conditions appeared to improve gastrointestinal tolerability (Section [2.2.2.1](#)). For this reason, as well as for consistency across the study population, participants in this study will be advised to take lerociclib after eating.

5.4. Screen Failures

A screen failure occurs when a participant who consents to participate in the clinical study is not subsequently enrolled in the study. A minimal set of screen failure information is required to ensure transparent reporting of screen failure participants to meet the CONSORT publishing requirements and to respond to queries from regulatory authorities. Minimal information collected for this study will include informed consent date, demography, screen failure details, eligibility criteria, and any SAEs.

Individuals who do not meet the criteria for participation in this study (screen failures) may be re-screened if their eligibility characteristics have changed.

If a participant fails to enroll during the 42-day Screening Period, a new participant number will be assigned at the time of re-screening, if applicable. Participants may not be entered into this study more than once.

5.4.1. Screening and Enrollment Log and Participant Identification Numbers

The participant's enrollment will be recorded in the Screening and Enrollment Log.

Upon enrollment (ie, at the time of signing the ICF), each participant will receive a unique participant identification number. This number is assigned by the IRT system. Participant numbers must not be re-used for different participants.

Each participant will be provided with a participant identification card on Day 1 of Cycle 1. This card will contain study site contact information to be used in the event of an emergency. Refer to Section 8 for details.

6. STUDY INTERVENTION(S) AND CONCOMITANT THERAPY

Study intervention is defined as any investigational intervention(s), marketed product(s), placebo, or medical device(s) intended to be administered to a study participant according to the study protocol.

6.1. Study Intervention(s) Administered

All study participants will receive lerociclib (referred to herein as the IMP) every 28 days (± 2 days), and will also receive Investigator's choice of either letrozole or fulvestrant (referred to herein as NIMPs).

All premenopausal or perimenopausal female participants, and all male participants, must be receiving goserelin for at least 28 days prior to entering the study and will remain on goserelin throughout the study, in accordance with the prescribing information and according to the study site's standard practice. The schedule for administration of goserelin for each individual participant is decoupled from the rest of the study visit schedule, and will be determined by the date of the participant's most recent dose of goserelin at the time of study entry (with "goserelin C1D1" defined as the date of the participant's most recent dose + 28 days, then every 28 days subsequently).

Details of the study interventions are provided in [Table 4](#).

Table 4: Study Intervention(s) Administered

| Intervention Label | Lerociclib | Letrozole | Fulvestrant | Goserelin |
|---------------------------------|--|--|---|--|
| Intervention Name | Lerociclib | Letrozole | Fulvestrant | ZOLADEX (goserelin acetate implant) – for pre- or perimenopausal female study participants and male participants |
| Intervention Description | Tablet taken orally, 50 mg or 150 mg, BID or as indicated in Section 6.5 | Tablet taken orally, 2.5 mg, QD | 500 mg, intramuscular injection, Q2W for initial 3 doses, then Q4W thereafter | Subcutaneous implant, 3.6 mg, Q4W |
| Type | Drug | Drug | Drug | Drug |
| Dosage Formulation | Tablet | Tablet | Solution | Implant |
| Unit Dose Strength(s) | 50 mg, 150 mg | 2.5 mg | 50 mg/mL | 3.6 mg |
| Dosage Level(s) | Starting dose: 150 mg BID or as indicated in Section 6.5 | 2.5 mg QD | Initial dose: 500 mg Q2W (Week 1 Day 1, Week 3 Day 1, Week 5 Day 1) Maintenance dose: 500 mg Q4W | 3.6 mg Q4W |
| Route of Administration | Oral | Oral | Intramuscular | Subcutaneous |
| Use | Experimental | Background intervention | Background intervention | Background intervention |
| IMP or NIMP | IMP | NIMP | NIMP | NIMP |
| Manufacturer | EQRx International, Inc. | STADApHarm GmbH and G Pharma Specialities Limited (ex-US) and Accord Healthcare (US) | EVER Neuro Pharma GmbH (ex-US) and Nanjing King-Friend Biochemical Pharmaceutical Co., Ltd. (US) | AstraZeneca AB (ex-US) and TerSera Therapeutics (US) |
| Sourcing | Provided centrally by the Sponsor | Provided centrally by the Sponsor | Provided centrally by the Sponsor | Provided centrally by the Sponsor |

Table 4: Study Intervention(s) Administered (Continued)

| Intervention Label | Lerociclib | Letrozole | Fulvestrant | Goserelin |
|-------------------------------|--|--|---|---|
| Packaging and Labeling | Lerociclib will be provided in 60-cc bottles sealed with 33-mm child-resistant caps with 35 tablets per bottle. Each bottle will be labeled as required per country requirement. | Letrozole will be provided as 30-count blister pack (ex-US) or 30-count bottle (US) and will be labeled as required per country requirement. | Fulvestrant will be provided as 2 × 250 mg/5 mL syringe per carton and will be labeled as required per country requirement. | Goserelin (ZOLADEX) will be provided as a single 3.6-mg injection implant per carton and will be labeled as required per country requirement. |

BID = twice daily; IMP = investigational medicinal product; NIMP = non-investigational medicinal product; Q2W = once every 2 weeks; Q4W = once every 4 weeks; QD = once daily; US = United States.

6.2. Preparation, Handling, Storage, and Accountability

Bottles of lerociclib tablets will be labeled and supplied to the pharmacist/designee, who will inventory the contents and document them according to the drug accountability requirements.

Dispensing instructions will be provided in the pharmacy manual and will be maintained in the pharmacy records.

All study interventions will be stored in a locked cabinet/secure area under applicable storage conditions at the site. Only the pharmacist/designee and designated personnel will have access to the IMP (lerociclib). Lerociclib tablets of all strengths are to be stored at the conditions specified in the EQ132-201 Pharmacy Manual.

The pharmacist/designee will verify the integrity of the clinical study supplies (storage conditions, correct amount received, condition of shipment, kit numbers, etc.) according to the Investigator site's SOPs.

At a minimum, the following data will be tracked on the drug accountability log at the site pharmacy:

- Date received
- Lot number
- Bottle number
- Date dispensed
- Participant number
- Identification of the person dispensing the drug
- Date returned

Records of study medication (used, lost, destroyed, and returned containers, individual bottles) should be made at each visit in the drug accountability and dispensing forms. Drug accountability and reconciliation will be checked and verified by the designated site staff during the study and by the site monitor during and at the completion of the study.

Once the site monitor has verified drug accountability at the site, any used drug remaining at the completion of the study will be destroyed. Unused and unopened study medication can be returned by the site monitor to the Sponsor at any point in the study. Please contact the Sponsor for further questions regarding drug accountability.

The Investigator or designee must maintain a log to confirm appropriate temperature conditions have been maintained during transit and storage for all study intervention received, and any discrepancies are reported and resolved before use of the study intervention.

Only participants enrolled in the study may receive study intervention, and only authorized site staff may supply or administer study intervention. All study interventions must be stored in a secure, environmentally controlled, and monitored (manual or automated) area in accordance with the labeled storage conditions with access limited to the Investigator and authorized site staff.

The Investigator, institution, or the head of the medical institution (where applicable) is responsible for study intervention accountability, reconciliation, and record maintenance (eg, receipt, reconciliation, and final disposition records).

Further guidance and information for the final disposition of unused study intervention are provided in the pharmacy manual.

6.3. Measures to Minimize Bias: Randomization and Blinding

There are no specific measures to minimize bias as this is an open-label, single-arm study with no comparator. All participants will receive lerociclib.

6.4. Study Intervention Compliance

When participants are dosed at the site, they will receive study intervention (NIMP or IMP) directly from the Investigator or designee, under medical supervision. The date and time of each dose administered in the clinic will be recorded in the source documents. The dose of study intervention (NIMP or IMP) and study participant identification will be confirmed at the time of dosing by a member of the study site staff other than the person administering the study intervention. Study site staff will examine each participant's mouth to ensure that the study intervention was ingested.

When participants self-administer study intervention(s) at home, compliance with study intervention will be assessed at each visit. Compliance will be assessed by counting returned tablets during the site visits and documented in the source documents and relevant form. Deviation(s) from the prescribed dosage regimen should be recorded.

Note: Any participants whose compliance with any study intervention falls below 80% may potentially be discontinued from study treatment. Any such cases are to be discussed by the Investigator and Sponsor before a final decision is made. Refer to Section [7.2.1](#) for details.

A record of the quantity of all study interventions dispensed to and administered by each participant must be maintained and reconciled with study intervention and compliance records. Intervention start and stop dates, including dates for intervention delays and/or dose reductions will also be recorded.

6.5. Dose Modification

6.5.1. Lerociclib

A participant may temporarily discontinue from study treatment with lerociclib for a duration of up to 14 days, for any reason. However, any such temporary discontinuations must be reported to the Medical Monitor. Refer to Section [7.1.2](#) for details.

This protocol allows some alteration from the currently outlined lerociclib dosing schedule, but the maximum daily dose will not exceed 300 mg. Dose adjustments of lerociclib for toxicities are to be made according to the organ system showing the greatest degree of drug-related toxicity. Toxicities will be graded using NCI CTCAE v5.0.

No more than 2 lerociclib dose-level reductions in total are allowed for any participant. Toxicity that requires dose-level reduction more than twice will lead to permanent discontinuation of lerociclib dosing for the individual participant. No lerociclib dose re-escalations are allowed if the dose reduction was due to a lerociclib-related toxicity.

In cases where the relationship to lerociclib is unclear, the Investigator may re-challenge the participant after discussion with the Medical Monitor.

Dose reduction will only be performed if the symptom(s) is (are) related to lerociclib in the opinion of the Investigator and not related to the underlying disease. The dose level reductions below will be utilized for the purpose of lerociclib modifications for toxicities.

Table 5: Lerociclib Dose Modifications

| Dose Level | Lerociclib Dose |
|-----------------------|-----------------------|
| Starting dose | 150 mg BID |
| First dose reduction | 100 mg BID |
| Second dose reduction | 50 mg QAM, 100 mg QPM |

BID = twice daily; QAM = once every morning; QPM = once every evening.

An off-drug period of up to 14 days is permitted to allow recovery from any toxicity in order to meet the continuation criteria.

6.5.1.1. Dose Modifications for Hematologic Toxicity

Table 6: Lerociclib Dose Modifications for Hematologic Toxicity

| Grade of Hematologic Toxicity (per NCI CTCAE v5.0) ^a | Lerociclib Dose Adjustment |
|--|---|
| Grade 3 (any Grade 3 hematologic toxicity except those listed below) | Continue lerociclib and repeat CBC at next scheduled visit or within 7 days. No dose reduction required. Starting at Cycle 5 Day 1, participants with stable Grade 3 neutropenia may have the frequency of CBC monitoring reduced to a different frequency determined by Investigator, if approved by the Medical Monitor. |
| Grade ≥ 3 neutropenia (ANC ≥ 500 to $< 1000/\text{mm}^3$) associated with a documented infection or fever $\geq 38.5^\circ\text{C}$ or Grade ≥ 3 thrombocytopenia (platelets $< 50,000$ to $25,000/\text{mm}^3$) associated with bleeding | Withhold lerociclib and monitor counts weekly until ANC $\geq 1 \times 10^9/\text{L}$ OR platelet count $\geq 75 \times 10^9/\text{L}$ with no further bleeding. Resume therapy at the next lower dose. If no further dose reduction is possible (participant is already receiving the lowest dose), lerociclib treatment must be discontinued. |
| Grade 4 | Withhold lerociclib until the hematological toxicity has recovered to Grade ≤ 2 . Resume therapy at the next lower dose. If no further dose reduction is possible (participant is already receiving the lowest dose), lerociclib treatment must be discontinued. |

^a. Applies to all hematologic adverse reactions, except lymphopenia (unless associated with clinical events, eg, opportunistic infections).

ANC = absolute neutrophil count; CBC = complete blood count; NCI CTCAE v5.0 = National Cancer Institute Common Terminology Criteria for Adverse Events, version 5.0.

The optimal treatment for IMP-induced neutropenia is to withhold lerociclib. Granulocyte colony-stimulating factor will not work in this setting because lerociclib induces a G₁ cell cycle arrest that cannot be overcome by G-CSF. Withholding lerociclib treatment will allow neutrophils to recover naturally.

Neutrophil counts should increase as the lerociclib concentrations in the body decline and the neutrophils are released from G₁ arrest.

If the participant experiences neutropenia lasting more than 10 days after the cessation of lerociclib, and the Investigator believes that G-CSF use is clinically indicated, then the Investigator must contact the Medical Monitor to discuss the use of G-CSF for that participant.

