2.3.2. Risk Assessment

Table 2: Risk Assessment

| Potential Risk of Clinical Significance | Summary of Data/Rationale for Risk | Mitigation Strategy |
|---|--|---|
| ILD/pneumonitis | There is an identified increased susceptibility to ILD/pneumonitis. Please refer to the lerociclib IB and DSUR for full details. | ILD appears to be a rare side effect of CDK4/6 inhibitor therapy. While there are no known risk factors for the development of ILD, participants who demonstrate symptoms related to pneumonitis (cough, dyspnea, chest pain, fever) should be promptly evaluated and treated effectively. Holding of lerociclib is necessary if there is clinical concern for pneumonitis. Participants may require steroid administration, as well. |
| Febrile neutropenia | There is a small risk of the development of febrile neutropenia. | If a participant is suspected of febrile neutropenia, lerociclib should be held. Neutropenia from CDK4/6 inhibitors does not respond to G-CSF. Supportive care should be provided as clinically indicated while the participant's counts recover. Following the resolution of febrile neutropenia, a participant may continue lerociclib, with appropriate dose reduction as necessary. |
| Lerociclib | | |
| Neutropenia | Lerociclib has been demonstrated to cause a decline in neutrophil counts over the first 4–5 weeks of therapy. | Complications of neutropenia (infection, febrile neutropenia) are uncommon, and participants will be screened for potential complications at all study visits. |
| Gastrointestinal tolerability | Participants exposed to lerociclib commonly experienced transient diarrhea and nausea. | None of the TEAEs of diarrhea or nausea have been shown to be of Grade 4 or higher severity. Gastrointestinal side effects do respond to supportive therapy (anti-emetics, antidiarrheals). |

Table 2: Risk Assessment (Continued)

| Potential Risk of Clinical Significance | Summary of Data/Rationale for Risk | Mitigation Strategy |
|---|--|--|
| ILD/pneumonitis | Four of 140 study participants (2.9%) were diagnosed with ILD/pneumonitis based on clinical history and diagnostic findings. | Two study participants required hospitalization with no intensive care support. There were no fatal cases. There were no reports of ILD/pneumonitis in healthy participants. Caution should be taken for any participants with upper respiratory infection symptoms or dyspnea/hypoxemia. There should be a low threshold to re-image in such cases. |
| Study Procedures | | |

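### Table 6's row label and platelet range disagree, so the restart rule for Grade 4 thrombocytopenia with bleeding is unclear and may be the looser one; the complicated-neutropenia restart names only a count

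*Protocol*

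**What the plan says.** Table 6 in Protocol Section 6.5.1.1 has three rows.

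- **Row 1** takes every Grade 3 hematologic toxicity not singled out further down: "Continue lerociclib and repeat CBC at next scheduled visit or within 7 days. No dose reduction required".
- **Row 2** is labelled Grade ≥3. It covers neutropenia "associated with a documented infection or fever" of at least 38.5 °C, and thrombocytopenia with bleeding. The ranges printed beside the labels are ANC 500 to below 1000/mm³ and platelets below 50,000 to 25,000/mm³. The action is "Withhold lerociclib and monitor counts weekly until ANC" is at least 1 × 10⁹/L, or platelets are at least 75 × 10⁹/L "with no further bleeding. Resume therapy at the next lower dose".
- **The Grade 4 row** reads "Withhold lerociclib until the hematological toxicity has recovered to Grade" 2 or lower, again with resumption one dose level down.

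The dose step, and the rule to stop if the participant is already at the lowest dose, are the same in row 2 and the Grade 4 row.

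The text below the table adds: "The optimal treatment for IMP-induced neutropenia is to withhold lerociclib".

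Table 2 in Section 2.3.2 treats febrile neutropenia separately. It says "If a participant is suspected of febrile neutropenia, lerociclib should be held", and then "Following the resolution of febrile neutropenia, a participant may continue lerociclib, with appropriate dose reduction as necessary". It gives no temperature.

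**The concern.** A dosing table should lead a site to one action for each event, and a worse event should not have an easier route back to drug. Here a participant who bleeds with platelets below 25 × 10⁹/L could be restarted at a lower count than one who bled at Grade 3, without any stated requirement that the bleeding has stopped.

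The neutropenia part of row 2 raises a related question. Infection or fever is what puts a participant in that row, yet the restart condition does not mention either, although the same cell requires bleeding to have stopped in the platelet case.

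Finally, a site working from Table 6 alone might continue dosing a participant whom Table 2 says to hold.

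What is at stake is the safety of individual participants. Section 2.3 lists both neutropenia and thrombocytopenia among the anticipated toxicities.

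**Working it through.** The plan gives no figure to reproduce. The check sets the rules side by side, using 1 × 10⁹/L = 1000/mm³.

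**Step 1: what Grade ≤2 and Grade 4 mean.** From the Grade 3 ranges printed in Table 6:
- Platelets: Grade ≤2 is at least 50 × 10⁹/L; Grade 4 is below 25 × 10⁹/L.
- ANC: Grade ≤2 is at least 1 × 10⁹/L.

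**Step 2: which row applies to bleeding with platelets below 25 × 10⁹/L.** By the Grade ≥3 label it fits row 2, and it also fits the Grade 4 row. By row 2's printed range it fits only the Grade 4 row. Section 6.5.1 tells sites to follow the organ system with the greatest toxicity, but that does not choose between two hematologic rows.

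**Step 3: compare the restart rules.**

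| | Row 2 | Grade 4 row | Difference |
|---|---|---|---|
| Platelets | ≥75 × 10⁹/L | ≥50 × 10⁹/L | 75 − 50 = 25 × 10⁹/L; 25/75 = 33% |
| Bleeding | must have stopped | not mentioned | condition absent |
| Count interval | weekly | not stated | interval absent |
| ANC | ≥1 × 10⁹/L | ≥1 × 10⁹/L | 0 |

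The Grade 4 platelet threshold is half the entry requirement of 100 × 10⁹/L in Section 5.1 (50/100). For neutrophils the two thresholds are equal, so the inversion concerns platelets only.

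**Step 4: does another section require bleeding, fever or infection to have resolved?**
- Section 6.5.1.2 holds drug for non-hematologic toxicity of Grade ≥3 that persists despite treatment, and allows restart at Grade ≤2. Ongoing Grade 2 bleeding or infection would pass.
- Section 7.1.2 leaves restart within 14 days to the Investigator, with notice to the Medical Monitor.
- Section 7.1.3 needs the toxicity to be resolving to Grade 2 or better, with the Medical Monitor's permission.
- Section 8.2.4 requires repeat testing of clinically significant abnormal laboratory values. It sets no restart condition.
- Table 2 speaks of continuing once febrile neutropenia has resolved.

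None requires bleeding to have stopped. For neutropenia, Table 2 and Section 6.5.1.2 cover part of the ground. What remains is mainly documented infection that is neither febrile neutropenia nor Grade ≥3.

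**Step 5: Table 2 against row 1.** Take Grade 3 neutropenia, no documented infection, and a fever below 38.5 °C that still raises suspicion of febrile neutropenia. Table 2 says hold; row 1 says continue. The documents do not define febrile neutropenia by temperature, so the width depends on an assumed starting point:
- 38.0 °C (the screening limit in Section 5.2, borrowed as a marker): 38.5 − 38.0 = 0.5 °C.
- 38.3 °C (assumed): 38.5 − 38.3 = 0.2 °C.
- 38.5 °C (assumed): no conflict.

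**Step 6: frequency.** At 150 mg BID, Section 4.3 reports one Grade 3 febrile neutropenia, one Grade 4 neutropenia and no further Grade 4 event attributed to lerociclib. It gives no denominator, so incidence cannot be estimated.

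**The case against.** The strongest reply is that row 2's label already includes Grade 4 and that row 2, which names the complication, is the more specific row. If both rows apply they do not collide: platelets of at least 75 × 10⁹/L without bleeding also satisfy Grade ≤2, so a careful site can follow row 2 and meet both. This stands as far as it goes. A reader might infer that the protocol plainly assigns the looser rule to Grade 4 bleeding; the documents do not support that, because it holds only if the printed range overrides the label. They do not make row 2 prevail either.

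A reader might also infer that any participant with complicated neutropenia can be restarted on the count alone. That is too broad. Table 2 refers to resolution, Section 6.5.1.2 reaches persistent Grade ≥3 infection, and Table 6 sets a threshold without compelling anyone to dose.

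Nor do the documents establish a hold-versus-continue conflict of known width. The 38 °C figure is a screening criterion. A site that holds on suspicion breaches nothing, since up to 14 days off drug is allowed and the text under Table 6 favors withholding. Those provisions permit a hold, however; they do not direct one against row 1's instruction to continue.

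It is also fair that the Grade 4 row lacks a stated interval for counts rather than monitoring altogether. Section 8.2.4 requires repeats, and recovery cannot be shown without them.

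Finally, Section 8 sends immediate safety concerns to the Sponsor, and Section 7.1.1 stops treatment for unacceptable risk. These are general safeguards and do not repair the specific rule.

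**Conclusion.** The point holds in a limited form. Row 2's label and printed platelet range disagree, and Grade 4 thrombocytopenia with bleeding has two candidate restart rules with no stated precedence. On the printed-range reading, the more severe event may restart at a platelet count 25 × 10⁹/L lower, with no bleeding condition. This rests only on the ranges in Table 6 itself.

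The neutropenia gap is real but narrower because other text partly covers it. The possible conflict between Table 2 and row 1 is the weakest part: its width is unknown and could be zero.

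Few participants should be affected, and the effect on study summaries is negligible. The correction is still worth making, because this is a dosing rule and the harm it could allow is re-dosing someone who is still bleeding or infected.

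**What to change.** Amend the text as follows:

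1. In row 2, print ANC below 1000/mm³ and platelets below 50,000/mm³, so that it covers Grade 3 or 4 with the named complications. Limit the Grade 4 row to Grade 4 without them.
2. Give row 2 two separate restart lines: ANC at least 1 × 10⁹/L with fever and infection resolved; platelets at least 75 × 10⁹/L with no further bleeding.
3. State in Table 6 that suspected febrile neutropenia is held pending evaluation, and have Table 2 refer to Table 6.

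Leave the dose-reduction steps and the discontinuation rule unchanged.

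The cost is wording in one table and one risk row, with no added participants or scheduled visits. The downside is a longer hold for Grade 4 thrombocytopenia with bleeding. In rare cases this could pass the 14-day limit in Section 7.1.2, after which lerociclib may not be restarted. From just under 25 × 10⁹/L, restarting by day 14 needs an average rise of (75 − 25)/14 = 3.6 × 10⁹/L per day, against (50 − 25)/14 = 1.8 under the lower threshold. From an assumed nadir of 10 × 10⁹/L the figures are (75 − 10)/14 = 4.6 and (50 − 10)/14 = 2.9. Weekly counts give two checks within the limit, on days 7 and 14.
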